## **10.3. Appendix 3: AEs and SAEs: Definitions and Procedures for Recording, Evaluating, Follow-up, and Reporting**

### **10.3.1. Definition of AE**

#### **AE Definition**

An AE is defined as any untoward medical occurrence associated with the use of a drug/vaccine in humans, whether or not considered related to the drug/vaccine.

#### **Events Meeting the Adverse Event Definition**

Exacerbation of a chronic or intermittent pre-existing condition including an increase in frequency and/or intensity of the condition, after the study intervention.

- New conditions detected or diagnosed after the study intervention even though they may have been present before the start of the clinical trial.

#### **Events NOT Meeting the Adverse Event Definition**

- Procedures planned before study entry (eg, hospitalization for preplanned surgical procedure).
- Medical or surgical procedure (eg, endoscopy, appendectomy): the condition that leads to the procedure should be the AE.
- Situations in which an untoward medical occurrence did not occur (social and/or convenience admission to a hospital).

An unsolicited AE (Section 10.3.4) is any AE reported by the participant that is not specified as a solicited AR in the protocol or is specified as a solicited AR in the protocol but starts outside the protocol-defined period for reporting solicited ARs (ie, for the 7 days after vaccination).

### **10.3.2. Definition of Serious Adverse Events**

An AE (including an AR) is considered an SAE if, in the view of either the Investigator or Sponsor, it results in any of the following outcomes:

- **Results in death**

A death that occurs during the clinical trial or that comes to the attention of the Investigator during the protocol-defined follow-up period must be reported to the Sponsor, whether or not it is considered related to study intervention.

- **Is life-threatening**

An AE is considered life-threatening if, in the view of either the Investigator or the Sponsor, its occurrence places the participant at immediate risk of death. It does not include an AE that, had it occurred in a more severe form, might have caused death.

- **Inpatient hospitalization or prolongation of existing hospitalization**

In general, inpatient hospitalization indicates the participant was admitted to the hospital or emergency ward for at least 1 overnight stay for observation and/or treatment that would not have been appropriate in the physician's office or outpatient setting. The hospital or emergency ward admission should be considered an SAE

regardless of whether opinions differ as to the necessity of the admission. Complications that occur during inpatient hospitalization will be recorded as AEs; however, if a complication/AE prolongs hospitalization or otherwise fulfills SAE criteria, the complication/AE will be recorded as a separate SAE. Procedures planned before study entry (eg, hospitalization for preplanned surgical procedure) are not considered SAEs.

- **Persistent or significant incapacity or substantial disruption of the ability to conduct normal life functions**

This definition is not intended to include experiences of relatively minor medical significance such as uncomplicated headache, nausea/vomiting, diarrhea, influenza, and accidental trauma (eg, sprained ankle) which may interfere with or prevent everyday life functions but do not constitute a substantial disruption.

- **Congenital anomaly or birth defect.**

- **Medically important event**

Medical judgment should be exercised in deciding whether SAE reporting is appropriate in other situations, such as important medical events that may not be immediately life-threatening or result in death or hospitalization but may jeopardize the participant or require medical or surgical intervention to prevent one of the other outcomes listed in the above definition. These events should usually be considered serious. Examples of such medical events include allergic bronchospasm requiring intensive treatment in an emergency room or at home, blood dyscrasias or convulsions that do not result in inpatient hospitalization, or the development of drug dependency or drug abuse.

### 10.3.3. **Solicited Adverse Reactions**

Solicited ARs are predefined local (at the injection site) and systemic events/symptoms that participants are specifically asked, and which are noted by the participant in their eDiary.

The solicited ARs for this clinical trial include selected signs and symptoms that are typically associated with vaccine reactogenicity. Reactogenicity refers to the occurrence and intensity of local and systemic ARs commonly following vaccination. The eDiary will solicit daily participant reporting of ARs using a structured checklist ([Section 8.3.10](#)). Participants will record such occurrences in an eDiary on the day of vaccination and for the 6 days after the day of dosing.

Severity grading of reactogenicity will occur automatically based on participant entry into the eDiary according to the grading scales presented in [Table 13](#) modified from the Toxicity grading scale for healthy adult and adolescent volunteers enrolled in preventive vaccine clinical trials ([DHHS 2007](#)). All solicited ARs (local and systemic) will be considered causally related to dosing.

Study sites will distribute Sponsor-provided oral thermometers and rulers for use by participants to assess body temperature and injection site reactions, respectively, for recording solicited ARs in the eDiaries. Based on availability, smartphone devices may be provided to those participants who do not have their own device to use for eDiary activities.

**Table 13:   Solicited Adverse Reactions and Grades**

Reaction	Grade 0	Grade 1	Grade 2	Grade 3	Grade 4
Injection site pain	None	Does not interfere with activity	Interferes with activity	Prevents daily activity	Requires emergency room visit or hospitalization
Injection site erythema (redness)	<25 mm/ <2.5 cm	25 to 50 mm/ 2.5 to 5 cm	51 to 100 mm/ 5.1 to 10 cm	>100 mm/ >10 cm	Necrosis or exfoliative dermatitis
Injection site swelling/induration (hardness)	<25 mm/ <2.5 cm	25 to 50 mm/ 2.5 to 5 cm	51 to 100 mm/ 5.1 to 10 cm	>100 mm/ >10 cm	Necrosis
Axillary (underarm) swelling or tenderness ipsilateral to the side of injection	None	No interference with activity	Some interference with activity	Prevents daily activity	Emergency room visit or hospitalization
Headache	None	No interference with activity	Some interference with activity	Prevents daily activity	Requires emergency room visit or hospitalization
Fatigue	None	No interference with activity	Some interference with activity	Prevents daily activity	Requires emergency room visit or hospitalization
Myalgia (muscle aches all over body)	None	No interference with activity	Some interference with activity	Prevents daily activity	Requires emergency room visit or hospitalization
Arthralgia (joint aches in several joints)	None	No interference with activity	Some interference with activity	Prevents daily activity	Requires emergency room visit or hospitalization
Nausea/vomiting	None	No interference with activity or 1 to 2 episodes/ 24 hours	Some interference with activity or >2 episodes/ 24 hours	Prevents daily activity, requires outpatient intravenous hydration	Requires emergency room visit or hospitalization for hypotensive shock

Reaction	Grade 0	Grade 1	Grade 2	Grade 3	Grade 4
Chills	None	No interference with activity	Some interference with activity not requiring medical intervention	Prevents daily activity and requires medical intervention	Requires emergency room visit or hospitalization
Fever (oral)	<38.0°C <100.4°F	38.0 to 38.4°C 100.4 to 101.1°F	38.5 to 38.9°C 101.2 to 102.0°F	39.0 to 40.0°C 102.1 to 104.0°F	>40.0°C >104.0°F

Note: Events listed above but starting >7 days post study intervention administration will be recorded on the AE page of the electronic case report form (eCRF). Causality for each event will be determined per assessment by the Investigator.

Any solicited AR that meets any of the following criteria must be entered into the participant's source document and must also be recorded in the participant's Reactogenicity eCRF:

- Solicited local or systemic AR that results in a visit to an HCP (MAAE; [Section 10.3.4](#))
- Solicited local or systemic AR leading to the participant withdrawing from the clinical trial or the participant being withdrawn from the clinical trial by the Investigator (AE leading to withdrawal)
- Solicited local or systemic AR lasting beyond 7 days post-injection
- Solicited local or systemic AR that otherwise meets the definition of an SAE

Additionally:

- If a participant reported a solicited AR during the solicited period and did not record the event in the eDiary, the event should be recorded on the Reactogenicity page of the eCRF.
- If the event starts during the solicited period, but continues beyond 7 days after dosing, the participant should notify the site to provide an end date to close out the event on the Reactogenicity page of the eCRF.
- If the participant reported an event after the solicited period (ie, after Day 7), it should be recorded as an AE on the AE page of the eCRF.

#### 10.3.4. Definition of Unsolicited Adverse Events

An unsolicited AE is an AE that was not solicited using a participant eDiary and that is communicated by a participant who has signed the informed consent. Unsolicited AEs include serious and nonserious AEs.

- Potential unsolicited AEs may be medically attended (ie, symptoms or illnesses requiring a hospitalization, emergency room visit, or visit to/by a healthcare provider). The participants will be instructed to contact the site as soon as possible to report medically attended event(s), as well as any events that, though not medically

attended, are of participant concern. Detailed information about reported unsolicited AEs will be collected by qualified site personnel and documented in the participant's records.

- Unsolicited AEs that are not medically attended nor perceived as a concern by the participant will be collected during an interview with the participants and by review of available medical records at the next visit.

### **10.3.5. Medically Attended Adverse Events**

An MAAE is an AE that leads to an unscheduled visit to an HCP. This would include visits to a study site for unscheduled assessments (eg, rash assessment, abnormal laboratory follow-up, COVID-19 [Section 10.3.8]) and visits to HCPs external to the study site (eg, urgent care, primary care physician). Investigators will review unsolicited AEs for the occurrence of any MAAEs. An unscheduled visit for assessment of protocol-defined ILI is not considered an MAAE unless additional medical evaluation, including examinations/testing not required PP and/or treatment is provided during the visit. All MAAEs will be collected through the entire study period.

### **10.3.6. Adverse Events of Special Interest**

An AESI is an AE (serious or nonserious) of scientific and medical concern specific to the Sponsor's product or program for which ongoing monitoring and immediate notification by the Investigator to the Sponsor is required and documentation is in the form of a case narrative. Such events may require further investigation to characterize and understand them.

Section 10.4 (Appendix 4) provides a list of AESIs pertinent to this clinical trial.

All AESIs will be collected through the entire study period and must be reported to the Sponsor or designee immediately and in all circumstances within 24 hours of becoming aware of the event via the EDC. If a site receives a report of a new AESI from a study participant or receives updated data on a previously reported AESI at a time after the eCRF has been taken offline, then the site can report this information on a paper SAE/AESI form using the SAE Mailbox, or the SAE Fax line (Section 10.3.10).

#### **10.3.6.1. Anaphylaxis**

All suspected cases of anaphylaxis associated with study intervention administration should be recorded as an SAE, based on the criteria for a medically important event, unless the event meets other serious criteria. As an SAE, the event should be reported to the Sponsor or designee immediately and in all circumstances within 24 hours per Section 10.3.10. The Investigator will submit any updated anaphylaxis case data to the Sponsor within 24 hours of it being available. For reporting purposes, a participant who displays signs or symptoms consistent with anaphylaxis (as described below) should be reported as a potential case of anaphylaxis. This is provided as general guidance for Investigators and is based on the Brighton Collaboration case definition (Rüggeberg et al 2007).

Anaphylaxis is an acute hypersensitivity reaction with multi-organ system involvement that can present as, or rapidly progress to, a severe life-threatening reaction. It may occur following exposure to allergens from a variety of sources.

- Anaphylaxis is a clinical syndrome characterized by the following:
- Sudden onset AND
- Rapid progression of signs and symptoms AND
- Involves 2 or more organ systems, as follows:

**Skin/mucosal:** urticaria (hives), generalized erythema, angioedema, generalized pruritus with skin rash, generalized prickle sensation, and red and itchy eyes.

**Cardiovascular:** measured hypotension, clinical diagnosis of uncompensated shock, loss of consciousness or decreased level of consciousness, and evidence of reduced peripheral circulation.

**Respiratory:** bilateral wheeze (bronchospasm), difficulty breathing, stridor, upper airway swelling (lip, tongue, throat, uvula, or larynx), respiratory distress, persistent dry cough, hoarse voice, sensation of throat closure, sneezing, and rhinorrhea.

**Gastrointestinal:** diarrhea, abdominal pain, nausea, and vomiting.

#### 10.3.6.2. Myocarditis/Pericarditis/Myopericarditis

Any case that has either a high clinical index of suspicion for myocarditis or pericarditis, or which is considered to be a confirmed case of myocarditis, pericarditis, or myopericarditis, should be reported as an AESI. The event should also be reported as an SAE if it meets seriousness criteria (see [Section 10.3.2](#)). The CDC has developed a working case definition for myocarditis, pericarditis, and myopericarditis, which is provided to inform the evaluation of suspected cases (see [Section 10.3.6.2](#)). The CDC document is intended for guidance only; the Investigator is expected to apply medical judgment in the evaluation of suspected cases, which may be prompted by a participant reporting symptoms concerning for myocarditis and/or pericarditis (per the CDC case definition).

Similarly, the diagnostic work up (eg, ECG, echocardiogram) and laboratory testing (eg, troponin) outlined in the CDC definition should be considered as a guidance to the Investigator, and promptly obtained if considered clinically indicated in any participant with concerning signs/symptoms. Referral to a cardiologist should be considered in those with positive tests results or clinically significant symptoms without other identifiable causes. The Investigator must submit any updated myocarditis, pericarditis or myopericarditis case data to the Sponsor within 24 hours of it being available. Cases of myocarditis and pericarditis will be followed until resolution of symptoms and abnormal test findings. Participants with events of myocarditis and/or pericarditis should continue to be followed in the clinical trial for safety as per the protocol assuming consent is not withdrawn.

In the event that a case is evaluated for myocarditis, pericarditis, or myopericarditis, and the Investigator considers that the findings do not support the diagnosis of myocarditis, pericarditis, or myopericarditis, the case should not be reported as an AESI.

An independent Cardiac Event Adjudication Committee (CEAC) that includes cardiologists will review suspected cases of myocarditis and pericarditis to determine if they meet CDC criteria of “probable” or “confirmed” events and make recommendations to the Sponsor.

([Gargano et al 2021](#)). The CEAC operates under the rules of an approved charter. Details

regarding the CEAC composition, responsibilities, procedures, and frequency of data review is defined in its charter.

The CDC case definition is provided in [Section 10.7](#) (Appendix 7) as guidance.

#### 10.3.7. Influenza-Like Illness

A protocol-defined ILI is determined by the occurrence of at least 1 respiratory illness symptom concurrently with at least 1 systemic symptom or the occurrence of any 2 or more respiratory symptoms as defined below.

Respiratory Symptoms	Systemic Symptoms
Sore throat	Body temperature $>37.2^{\circ}\text{C}$ ( $>99^{\circ}\text{F}$ )
Cough/rhinorrhea/nasal congestion ( $\geq 1$ of the 3 symptoms count as 1 respiratory symptom)	Chills
Sputum production	Tiredness
Wheezing	Headache
Difficulty breathing	Myalgia
	Nausea/Vomiting
	Diarrhea

A CDC-defined ILI is defined as body temperature  $\geq 37.8^{\circ}\text{C}$  ( $100^{\circ}\text{F}$ ) accompanied by a cough and/or sore throat.

An RT-PCR-confirmed ILI is defined as a positive influenza result by RT-PCR done at any setting during the study period.

#### 10.3.8. Suspicion of SARS-CoV-2 Infection

SARS-CoV-2 should be suspected if the participant experiences any one of the symptoms listed below lasting at least 48 hours (except for fever and/or respiratory symptoms) ([CDC 2020b](#)):

- Fever (temperature  $\geq 38.0^{\circ}\text{C}$  [ $100.4^{\circ}\text{F}$ ]) or chills (of any duration, including  $\leq 48$  hours)
- Cough (of any duration, including  $\leq 48$  hours)
- Shortness of breath and/or difficulty breathing (of any duration, including  $\leq 48$  hours)
- Fatigue
- Muscle or body aches
- Headache
- New loss of taste and/or smell
- Sore throat, congestion, or runny nose
- Nausea or vomiting
- Diarrhea

Symptomatic COVID-19 is defined by the presence of one of the CDC-listed symptoms ([CDC 2020c](#)) and a positive RT-PCR test on a respiratory sample. Asymptomatic SARS-CoV-2

infection is defined as a positive RT-PCR test on a respiratory sample in the absence of symptoms or a positive serologic test for antinucleocapsid antibody after a negative test result at the time of enrollment, with the serologic assay detecting previously resolved SARS-CoV-2 infections that may have occurred between visits, and the RT-PCR to detect active viral infection at the time of a visit. If participants are confirmed to have SARS-CoV-2 infection and are symptomatic or asymptomatic, the Investigator will notify the participants' primary care physicians of the diagnosis and the local public health authorities as required per local regulations.

If the participant had known exposure to COVID-19 (eg, exposure to someone with a confirmed case of COVID-19), it will be captured in the COVID-19 exposure form, and the participant will continue to follow all remaining study assessments as scheduled. Likewise, participants with a confirmed case of COVID-19 will continue to follow all remaining study assessments as scheduled.

### **10.3.9. Recording and Follow-Up of AE and/or SAE**

The Investigator and any qualified designees are responsible for detecting, documenting, and recording events that meet the definition of an AE, including SAEs, and remain responsible for following up AEs until resolution, stabilization, the event is otherwise explained, or the participant is LTFU, as defined in [Section 7.3](#).

All unsolicited AEs reported or observed during the clinical trial will be recorded on the AE page of the eCRF. All unsolicited AEs will be collected from start of study intervention through 28 days after injection.

All SAEs reported or observed during the clinical trial will be recorded on the SAE page of the eCRF. All SAEs will be collected from the start of study intervention until EoS visit at the timepoints specified in the SoA ([Table 1](#)).

Information to be collected includes type of event, time of onset, Investigator-specified assessment of severity and relationship to study intervention, time of resolution of the event, seriousness, as well as any required treatment or evaluations, and outcome. The unsolicited AEs resulting from concurrent illnesses, reactions to concurrent illnesses, reactions to concurrent medications, or progression of disease states must also be reported. All AEs will be followed until they are resolved or stable or judged by the Investigator to be not clinically significant. The MedDRA will be used to code all unsolicited AEs.

After the initial AE/SAE report, the Investigator is required to proactively follow each participant at subsequent visits/contacts. All AEs, SAEs, and AEs of special interest (as defined in [Section 10.3.6](#)) will be followed until resolution, stabilization, the event is otherwise explained, or the participant is LTFU (as defined in [Section 7.3](#)). Further information on follow-up procedures is provided in [Section 10.3](#).

#### **10.3.9.1. Assessment of Intensity**

The severity (or intensity) of an AR or AE refers to the extent to which it affects the participant's daily activities. The Toxicity Grading Scale for Healthy Adult and Adolescent Volunteers Enrolled in Preventive Vaccine Clinical Trials ([DHHS 2007](#)) will be used to categorize local and systemic reactogenicity events (solicited ARs), clinical laboratory test results, and vital sign

measurements observed during this clinical trial. Specific criteria for local and systemic reactogenicity events are presented in [Section 10.3.3](#).

The determination of severity for all unsolicited AEs should be made by the Investigator based upon medical judgment and the definition of severity as follows:

- **Mild:** These events do not interfere with the participant's daily activities.
- **Moderate:** These events cause some interference with the participant's daily activities and require limited or no medical intervention.
- **Severe:** These events prevent the participant's daily activity and require intensive therapeutic intervention.

Study staff (or delegate) should elicit from the participant, the impact of AEs on the participant's activities of daily living to assess severity and should document it appropriately in the participant's source documentation. Changes in the severity of an AE should be documented in the participant's source documentation to allow an assessment of the duration of the event at each level of intensity to be performed. An AE characterized as intermittent requires documentation of onset and duration of each episode. An AE that fluctuates in severity during the course of the event is reported once in the eCRF at the highest severity observed.

#### **10.3.9.2. Assessment of Causality**

The Investigator will assess causality (ie, whether there is a reasonable possibility that the study intervention caused the event) for all AEs and SAEs. The relationship will be characterized using the following classification:

- **Not related:** There is not a reasonable possibility of a relationship to the study intervention. Participant did not receive the study intervention, OR temporal sequence of the AE onset relative to administration of the study intervention is not reasonable, OR the AE is more likely explained by another cause than the study intervention.
- **Related:** There is a reasonable possibility of a relationship to the study intervention. There is evidence of exposure to the study intervention. The temporal sequence of the AE onset relative to the administration of the study intervention is reasonable. The AE is more likely explained by the study intervention than by another cause.

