**Table 11: Analysis Strategy for Safety Parameters**

Safety Endpoint	Number and Percentage of Participants	Number of Events	95% CI
Any solicited AR (overall and by local, systemic)	✓	—	✓
Any unsolicited AE	✓	✓	—
Any unsolicited treatment-related AE	✓	✓	—
Any SAE	✓	✓	—
Any treatment-related SAE	✓	✓	—
Any unsolicited AESI	✓	✓	—
Any unsolicited treatment-related AESI	✓	✓	—
Any unsolicited MAAE	✓	✓	—
Any unsolicited treatment-related MAAE	✓	✓	—
Any unsolicited severe AE	✓	✓	—
Any unsolicited treatment-related severe AE	✓	✓	—
Any unsolicited AE leading to withdrawal from study participation	✓	✓	—

Abbreviations: AE = adverse event; AESI = adverse event of special interest; AR = adverse reaction;

CI = confidence interval; MAAE = medically attended adverse event; SAE = serious adverse event.

Notes: 95% CI using the Clopper-Pearson method, ✓=results will be provided.

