#### **10.3.10. Reporting of SAEs**

Prompt notification by the Investigator to the Sponsor of an SAE is essential so that legal obligations and ethical responsibilities toward the safety of participants and the safety of a study intervention under clinical investigation are met.

Any AE considered serious by the Investigator or that meets SAE criteria ([Section 10.3.2](#)) must be reported to the Sponsor immediately (within 24 hours of becoming aware of the SAE) via the EDC. The Investigator will assess whether there is a reasonable possibility that the study intervention caused the SAE. The Sponsor will be responsible for notifying the relevant regulatory authorities of any SAE as required per the applicable regulations. The Investigator is responsible for notifying the IRB/IEC directly.

If the eCRF is unavailable at the time of the SAE, the event should be reported using the provided study-specific paper SAE/AESI Reporting Form and sent via the email address or fax number on the form.

Regulatory reporting requirements for SAEs are described in [Section 8.4.4](#).

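### Protocol 10.3.9.2 asks for a reasonable possibility but its categories turn on the likelier cause, so treatment-related counts may fall below the protocol's own standard

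*Protocol*

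**What the plan says.** Protocol 10.3.9.2 frames causality for every AE and SAE as "whether there is a reasonable possibility that the study intervention caused the event". The investigator must then use one of two categories.

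- **Not related** opens with "There is not a reasonable possibility of a relationship to the study intervention". Three alternatives follow, joined by OR: the vaccine was not given, the timing is not reasonable, or "the AE is more likely explained by another cause than the study intervention".
- **Related** opens with "There is a reasonable possibility of a relationship to the study intervention". Three further sentences follow, on exposure, on reasonable timing, and lastly "The AE is more likely explained by the study intervention than by another cause".

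Protocol 10.3.10 repeats the opening question for serious events without comparing causes: "The Investigator will assess whether there is a reasonable possibility that the study intervention caused the SAE".

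The classification feeds Protocol Table 11 (for example the row "Any unsolicited treatment-related AE"). It also feeds the treatment-related tables and listings in SAP 2.6.3.2 and its subsections, which SAP 3.6.3.2 applies to Part 2. Neither document provides an intermediate level, a rule for ties, or a statement that the opening sentence of a category overrides what follows it.

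**The concern.** The question and the answers use different thresholds. A reasonable possibility is a low bar, and several causes can clear it at once. Being the likelier explanation is a higher bar, and at most one cause can clear it. An investigator who follows the opening question and one who follows the category text can code the same event differently.

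Competing causes are to be expected here. Protocol 10.4 requires events of special interest to be reported even when they occur during or after COVID infection, so a rival explanation will sometimes be present. The scale is also binary: an event coded Not related because of the likelier-cause clause cannot be told apart afterwards, from the coded field, from one that was plainly unrelated.

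At stake is the meaning of the treatment-related safety outputs. Safety is a primary objective in both parts.

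**Working it through.** No arithmetic decides this point, so the texts are set side by side and every case is worked through.

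**Step 1: classify.** Take an exposed participant with reasonable timing and an event that the vaccine could reasonably have caused. Only the relative likelihood of the causes then varies. The two Not related columns cover both ways of reading that category.

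| Likelier cause | Stated question (10.3.9.2 opening, 10.3.10) | Related, all sentences required | Not related, one listed alternative suffices | Not related, opening sentence plus one alternative |
|---|---|---|---|---|
| Vaccine | yes | met | not met | not met |
| Equal | yes | not met | not met | not met |
| Other cause | yes | not met | met | not met |

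All three rows answer yes to the stated question, but only the first is Related. The second row has no category on either reading. The third is Not related on the natural reading, because of the explicit ORs, although that category's opening sentence is then false. On the stricter reading it has no category either.

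**Step 2: direction.** Events that satisfy the whole Related text form a subset of events with a reasonable possibility. Any count built on the category text is therefore equal to or lower than the count under the stated question, never higher.

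**Step 3: reach.** Table 11 has 12 rows, of which 5 depend on this coding: treatment-related AE, SAE, AESI, MAAE and severe AE. In the SAP the same coding drives the treatment-related lines of the overview (2.6.3.2.1), five of the system-organ-class tables (2.6.3.2.2), the treatment-related table by severity (2.6.3.2.4) and two listings (2.6.3.2).

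**Step 4: size.** Let f be the share of participants with a reasonably possible event who have no event meeting the full Related text. The share is taken per participant because SAP 2.6.3.2 counts each person at the strongest relationship level. The related count is then multiplied by (1 − f). The documents give no value for f.

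To show sensitivity only, start from the plan's own calculation. Table 9, n = 40 and rate 5%: 1 − 0.95^40 = 87.1%, which reproduces. That table concerns any AE, so using 5% as the rate of participants with a reasonably possible event is an assumption. The chance of at least one participant coded Related in an arm is 1 − (1 − 0.05 × (1 − f))^40:

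- f = 0: 87.1%
- f = 10%: 84.1%
- f = 25%: 78.3%
- f = 50%: 63.7%

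These values of f are assumed and none is a prediction.

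**The case against.** The best reply is that the opening sentences govern. Both categories begin with reasonable possibility, Related contains no AND, and the later sentences could be read as supporting considerations. On that reading the categories cover every event, and nothing is lost. Exact ties are also rare in a judgement of this kind, and investigators will disagree about ambiguous events under any wording.

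Part of this stands: if investigators code on the opening sentence, f is zero. But nothing tells them to. They are directed to use the classification, and beside the explicit ORs in Not related the sentences under Related read naturally as cumulative. The likelier-alternative case is also no rarity confined to exact ties.

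A reader might infer more than the documents support:

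- **That related events are under-counted.** Only the direction is shown. An actual shortfall needs events of the second or third kind, and investigators who apply the clause.
- **That ambiguous events go unseen.** Each of the five treatment-related rows has an all-causality partner in Table 11, all unsolicited AEs are listed, and Protocol 8.4.3 has AEs documented whatever the suspected cause.
- **That safety reporting or pausing is compromised.** SAEs and AESIs go to the sponsor within 24 hours without a causality filter (8.4.1, 10.3.10). The pause rules have their own attribution wording (Table 7), and all solicited reactions count as related (10.3.3). Protocol 8.4.4 and 10.3.10 leave regulatory notification to the sponsor under the applicable rules, and do not tie it to this code.
- **That ambiguity matters more because the vaccine is new to humans.** Protocol section 2 reports 630 mRNA-1083 recipients in Part 1 and about 4000 in Phase 3.
- **That one arm is favoured.** The same text applies to every arm of an observer-blind trial.

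**Conclusion.** The inconsistency is real and lies within a single section of the protocol. As written, Related is narrower than the standard that 10.3.9.2 announces and 10.3.10 repeats. Reasonably possible events with a likelier alternative are coded Not related, and ties have no category.

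The treatment-related counts for AEs, SAEs, AESIs, MAAEs and severe AEs may therefore be lower than under the protocol's own standard. They cannot be higher. This rests on reading the sentences under Related as cumulative. The documents do not allow the size to be estimated, and zero is possible. Total event capture, sponsor reporting, solicited reactions and pause rules are untouched, and safety is descriptive, so no test or error rate is involved. The wording should be corrected because the affected rows sit in the primary safety output and the correction is small.

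**What to change.** Reconcile 10.3.9.2 with 10.3.10 by making the opening sentence the sole test: Related means that there is a reasonable possibility, Not related means that there is not. Below the two categories, list exposure, timing and alternative causes as factors to consider in reaching that answer, not as conditions. Neither likelier-cause clause should remain a deciding criterion.

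Deleting the two clauses alone is not enough. If the remaining items are still read as conditions, an exposed and well-timed event with an obvious outside cause, such as a fracture in a road accident on Day 10, would meet neither category.

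Align the eCRF completion guidance, and state in each part's study report which definition was applied. Part 1 was enrolled in April to May 2023, and neither amendment's summary of major changes lists a change to 10.3.9.2, so Part 1 was presumably coded under the present text.

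The cost is a few sentences. The downsides are that somewhat more events will be coded Related, and that Parts 1 and 2 may end up on different definitions. The separate study reports make the second manageable if each states its definition.
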